8.5 Sample Size and Power Considerations of Primary, Co-Primary and Secondary Objectives

This study is planned using a group sequential design, with one or more interim analyses for futility and efficacy using O'Brien-Fleming efficacy and futility bounds. The statistical test performed will depend only on the number of confirmed ILI cases (events), so the sample size estimate is only for operational reasons (an estimate of number of subjects needed to assess the endpoint).

Primary Efficacy Objective ≥ 2 years to < 18 years of age

Estimated sample size to arrive at 298 events, is 4,814 evaluable subjects (or 2,407 evaluable subjects per treatment group), assuming attack rate in non-influenza comparator vaccine subjects of 8%, vaccine efficacy of 45%, and the risk of infection contained entirely within period covered by follow-up. Accounting for early dropout and uncertainty about the assumed parameters, 5,349 subjects are planned to be enrolled to demonstrate that the lower limit of the two-sided 95% CI for the VE is greater than 20% for the primary endpoint assessment, with approximately 90% power.

Co-primary Efficacy Objective ≥ 3 years to < 18 years of age

Assuming a true vaccine efficacy of 50% it was calculated that approximately 381 observed confirmed ILI cases would be needed to demonstrate that the lower limit of the two-sided 95% CI for the VE is greater than 30% with approximately 90% power.

The statistical test performed will depend only on number of confirmed ILI cases (events), so sample size estimate is only for operational reasons. Estimated sample size to arrive at 381 events, is 6,350 evaluable subjects (or 3,175 evaluable subjects per treatment group), assuming attack rate in non-influenza comparator vaccine subjects of 8%, assumed vaccine efficacy of 50%, VE is greater than 30%, and the risk of infection contained entirely within period covered by follow-up. Accounting for early dropout and uncertainty about the assumed parameters, 7,056 subjects are planned to be enrolled to demonstrate that the lower limit of the two-sided 95% CI for the VE is greater than 30%.

Table 8.5.1 summarizes the power calculations assumptions and the number of events required to meet primary and co-primary endpoint.

Table 8.5.1 Power calculation for Primary and Co-Primary Endpoints

Age group	VE Success Criteria	Assumed Vaccine Efficacy	Influenza attack rate in comparator group	Power	Minimal total evaluable subjects per Treatment Group	Minimal enrolled subjects needed per Treatment group*()	Minimal total Number Enrolled*	total Number of ILIs to demonstrate LL 95% CI for VE is > 30% or 20%
≥2 years to <18 years of age	20%	45%	8%	>90%	2,407	2,674	5,349	298
≥3 years to <18 years of age	30%	50%	8%	>90%	3,175	3,528	7,056	381

*accounted for early dropout and uncertainty

A provision for triggering a new cohort of subjects is also included, and is based on either attainment of an inadequate total number laboratory confirmed influenza case in both seasons, or paired with the outcome of an interim analysis (noted below).

Nasopharyngeal swab samples will be analyzed in batches and the number of laboratory confirmed influenza cases will be reviewed on a regular basis (blinded review). Following the end of the second influenza season, and after observing at least 50% of planned events meeting the co-primary endpoint, an interim analysis for efficacy and futility will be performed by a Data Monitoring Committee (DMC). Stopping rules for futility and efficacy and any additional details regarding the interim analysis will be specified in the DMC Charter and in the SAP.

For this analysis a restricted unblinding will be done, i.e. only external DMC members and Contract Research Organization (CRO) employees executing it will receive access to the randomization codes and unblinded data for the purpose of preparing the interim analyses.

Strata such as age group and history of previous vaccination will be accounted for in the final analysis as a covariate “strata” in proportional hazard’s model. The use of strata in such context does not affect sample size calculation.

To account for the sample size requirements to demonstrate that the lower limit of the two-sided 95% CI for the VE is greater than 30% in ≥ 3 to < 18 years old (co-primary objective) and the contributable 2 year plus enrolment for the co-primary objective, the total sample size is estimated to be minimally 7,692 subjects. While minimum enrolment for the 2+ age cohort will not be pre-defined a maximum of 635 subjects ($=7,692 - 7,056$) in this age group can be enrolled to maintain a power $> 90\%$ for the co-primary endpoint. Thus, in total minimally 7,692 subjects are planned be enrolled over the entire age distribution of ≥ 2 to < 18 years of age.

Sample Size for Secondary Immunogenicity Objectives (Immunogenicity Subset):

The immunogenicity study will be performed in the second season and subsequent seasons. The immunogenicity endpoint is descriptive and the number of subjects aged ≤ 2 to > 9 years of age is maximized at 444 subjects with approximately 400 evaluable subjects, per season for the second season and for the third season. With a 1:1 allocation, approximately 200 evaluable subjects will be enrolled from the active arm and 200 evaluable subject would be from the non-influenza active comparator arm. Assuming a 10% drop out rate approximately 444 subjects will be enrolled per season. For the subsequent seasons, the number of subjects enrolled into the immunogenicity subset is maximized at 200 evaluable subjects per season (100 from the active arm and 100 from the non-influenza comparator arm). Assuming a 10% drop out rate approximately 222 subjects will be enrolled per every subsequent season after season three (fourth season, fifth season, etc) depending on the duration of the study.

In the case of early study termination, in the event that the number of ILI cases has been reached, the total number of subjects evaluated may be lower than the number of evaluable subjects described per season.

Sample Size for Safety:

With a Safety Population of 2,674 evaluable subjects in the safety set of QIVc, AEs with population rates of 1 in 1,000 have a 93.1% probability of being detected.

Events with population rates of 1 in 893 have a 95% chance of being observed with $n=2,674$) Events with population rates of 1 in 2,000 have a 73.7% chance of being observed with $n=2,674$

Sample size calculations were performed using PASS v12.0.2.

8.6 Interim Analysis

As the circulation of influenza viruses is seasonal and the event rates of influenza are difficult to predict, this study is group sequentially, with a case count-driven interim analysis. The goal of the Interim Analyses is, first, to minimize the risk of not being able to take a significant test decision after the end of the study, and second, to be able to stop the study for early evidence of efficacy or for futility.

Primary Efficacy Analysis:

The number of laboratory confirmed influenza cases will be reviewed on a regular basis. After the majority of cases for the second season have been collected, and after observing at least 50% of planned events meeting the co-primary endpoint, an interim analysis for efficacy and futility will be performed by a DMC. The two influenza seasons are defined as the first 2 influenza seasons after study start but no later than through April 2018, guided by influenza seasonality and peak season in Northern Hemisphere.

- If the number of influenza cases is less or equal to 190 overall, no interim analysis for efficacy and futility will be done and the study will be extended because the probability to make a conclusion for futility or efficacy is too low.
- If the number of influenza cases is greater or equal to 191 but less than 381 an unblinded interim analysis for efficacy and futility will be performed by a DMC. To maintain the overall alpha, $\alpha = 2.5\%$ (1-sided), for the hypotheses testing for the primary objectives, an error-spending-function will be used. The benefit of using an error-spending-function is that no maximum number of analysis stages and the timing of the analyses need to be pre-specified, what in practice means that the duration of the study in terms of number of seasons can be left open. In this case α -boundaries, forming the adjusted probabilities for the type I error, are calculated using error-spending function and if the p-values for both primary objectives are lower than the respective α -boundary the trial stops early (i.e., without reaching the targeted number of cases of 381) for efficacy. Similarly β -boundaries are calculated, i.e. the adjusted probabilities for the type II error β , and if the p-values are higher than the β -boundaries, the trial stops early for futility at that stage. In other words the trials stops early for futility, when the data provides sufficient evidence that the alternative hypotheses is not true, i.e. that the test vaccine is not as good as expected. Otherwise, the trial continues enrollment. Decisions to stop or continue the trial will be made on the basis of discussions between the DMC and Senior Management.
- If the number of influenza cases is greater or equal to 381 (targeted number of cases to be able to evaluate the co-primary objective) the study will be unblinded

and the final analysis will be performed by the Sponsor. If the trial proceeds to the final analysis (upon reaching 381 cases) the boundaries for acceptance or rejection are identical to the assumed type I and type II errors for the overall design, and the trial stops to either reject or accept the null hypothesis of either one or / and the other of the primary objectives.

In case the DMC states that the observed data provides already the full information level needed for the final test decision, then the final analysis can be done on full alpha level (2.5 % 1-sided) and no further enrollment is needed. However if the decision of the group-sequential test is to continue the study then it is on the DMC to determine the number of subjects needed to be enrolled. The monitoring committee should not be influenced by the individual results of the vaccine groups observed at an interim analysis stage when planning further subjects' accrual or the times of future analysis. Only the overall number of cases is allowed to be used for further planning. The following formula for determination of sample sizes for further enrollment may be used:

$$N_{\text{total}} = (C_{\text{planned}} - C_{\text{observed}}) / [(ER_{\text{QIVc}} + ER_{\text{comp}})/2],$$

where N_{total} denotes the total number of subjects needed for further enrollment, C_{planned} is the overall number of cases needed for the test, i.e. 381 cases, C_{observed} are the at that stage observed number of cases overall, and ER are the respective event rates assumed for each group, i.e., 8,0% for non-influenza comparator group and 4,0% for QIVc. A consideration of early dropout and uncertainty about assumed parameters will be accounted for number of enrolled subjects. The method of stopping rules given above is statistical and should be completed by clinical and strategic stopping rules that allow the DMC to make a decision on a broader picture of the data which includes safety endpoints and the other endpoints of the study.

Stopping rules for futility and efficacy and any additional details regarding the interim analysis will be specified in the DMC Charter and in the SAP.

For the interim analyses, if needed, a restricted unblinding will be done, i.e., only DMC members and unblinded CRO employees responsible for the analyses will receive access to the randomization codes and unblinded data for the purpose of preparing the interim analyses (further information on handling of the blinding for the interim analyses can be found in section 3.3). The results of the interim analyses are only for DMC purposes and will not be reported in the Clinical Study Report (CSR).

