
associated with these events were used. The NP swab should be collected as soon as possible, preferably within 3 days, but up to 6 days following the onset of protocol defined ILI symptoms. In case ILI symptoms are present during a scheduled clinic visit, then the NP swab may be collected at this visit. NP swabs will be evaluated by RT-PCR and culture at a central laboratory, followed by characterization of the influenza strains as “vaccine strains” versus other influenza strains. RT-PCR and culture confirmed influenza cases will be evaluated within specific timeframes of first and second study vaccination.
 
Total length of subject participation is 180 days after last vaccination, or until the end of influenza season, whichever is longer.
 
Laboratory confirmed influenza cases will be reviewed on a regular basis (blinded review). After the majority of cases for the second season have been collected, and after observing at least 50% of planned events meeting the co-primary endpoint, an interim analysis for efficacy and futility will be performed by a Data Monitoring Committee (DMC). Stopping rules for futility and efficacy and any additional details regarding the DMC will be defined in the SAP and in the DMC Charter, including how the interim analysis will assess the primary objective. These two influenza seasons are defined as the first 2 influenza seasons after study start but no later than through April 2018, guided by influenza seasonality and peak season in Northern Hemisphere.
 
As the circulation of influenza viruses is seasonal and the rates of influenza are difficult to predict, this study is group sequentially designed with one or more interim analyses planned over the course of the study. The goal of Interim Analyses is, first, to minimize the risk of not being able to take a significant test decision after the end of the study, and second, to be able to stop the study for early evidence of efficacy or for futility after observing at least 191 of planned lab-confirmed influenza cases.
 
If the number of influenza cases is less or equal to 190 (minimum number of cases to indicate efficacy or futility), no interim analysis for efficacy and futility will be done and the study will be extended to an additional influenza season.
		

Name of Sponsor:	Protocol number:	Generic name of study vaccine(s):

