3.6 Stopping/Pausing Guidelines

NP swabs will be analyzed in batches on a rolling basis throughout the study. At least one interim analysis will be performed based on the number of RT-PCR or culture confirmed influenza cases accrued at the time of the first interim analysis. After periodic review of safety and efficacy data, the DMC will make a recommendation as to whether enrolment in the study should continue, be stopped or paused.

Independent of the DMC, the Sponsor can halt the study at any time. If the study is halted, the Sponsor or delegate will promptly notify the health authorities and investigators, who will promptly inform the study subjects and local Ethics Committee/ Institutional Review Board (EC/IRB) as per local regulations. Study vaccinations and further enrolment will only occur after written authorization is provided by the Sponsor in conjunction with a recommendation to proceed by the DMC and in consultation with the health authorities and EC/IRB, as appropriate.

There are no predetermined stopping rules other than circumstances for which subjects may not be eligible for additional study vaccinations as described in [section 4, Selection of Study Population](#) or may be withdrawn from the study according to the best interests of the subject as described in [Section 3.8, Premature Withdrawal from Study](#).

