14. INTERIM ANALYSIS

14.1 Interim Analysis

As the circulation of influenza viruses is seasonal and the event rates of influenza are difficult to predict, this study is group sequentially, with a case count-driven interim analysis if decided by the Sponsor. The goal of the Interim Analyses is, first, to minimize the risk of not being able to take a significant test decision after the end of the study, and second, to be able to stop the study for early evidence of efficacy.

The number of laboratory-confirmed influenza cases will be reviewed on a regular basis. If decided by the Sponsor and after observing at least 50% of planned events meeting the co-primary endpoint, an interim analysis for efficacy may be performed for evaluation by a DMC.

- If the number of RT-PCR confirmed influenza cases is less or equal to 190 overall, no interim analysis for efficacy may be done and the study will be extended because the probability to make a conclusion for efficacy is too low.
- If the number of RT-PCR confirmed influenza cases is greater or equal to 191 but less than 381 unblinded interim analyses for efficacy may be performed for evaluation by the DMC (see below for description and DMC charter). To maintain the overall alpha, $\alpha = 2.5\%$ (1-sided), for the hypotheses testing for the primary objectives, an error-spending-function will be used. The benefit of using an error-spending-function is that no maximum number of analysis stages and the timing of the analyses need to be pre-specified, what in practice means that the duration of the study in terms of number of seasons can be left open. In this case α -boundaries, forming the adjusted probabilities for the type I error, are calculated using error-spending function and if the p-values for both primary objectives are lower than the respective α -boundary the trial stops early (i.e., without reaching the targeted number of cases of 381) for efficacy. Otherwise, the trial continues enrollment. Decisions to stop or continue the trial will be made on the basis of discussions between the DMC and Senior Management.

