- If the number of RT-PCR confirmed influenza cases is greater or equal to 381 (targeted number of cases to be able to evaluate the co-primary objective) and subjects have been enrolled over at least three seasons the study will be unblinded and the final analysis will be performed by the sponsor. If the trial proceeds to the final analysis (upon reaching 381 cases) the boundaries for acceptance or rejection are identical to the assumed type 1 and type 2 errors for the overall design, and the trial stops to either reject or not reject the null hypothesis of the primary objective.

That is, the primary objective, i.e. VE against RT-PCR or culture confirmed influenza A and or B will be assess the one-sided 0.025 alpha level.

In case the DMC states that the observed data provides already the full information level needed for the final test decision, then the final analysis can be done on full alpha level of (2.5 % 1-sided) and no further enrollment is needed. If, however, the decision of the group-sequential test is to continue the study then it is on the DMC to determine the number of subjects needed to be enrolled. The DMC should not be influenced by the individual results of the vaccine groups observed at an interim analysis stage when planning further subjects' accrual or the times of future analysis. Only the overall number of cases is allowed to be used for further planning. The following formula for determination of sample sizes for further enrollment may be used:

$$N_{\text{total}} = (C_{\text{planned}} - C_{\text{observed}}) / [(ER_{\text{QIVc}} + ER_{\text{comp}})/2],$$

where N_{total} denotes the total number of subjects needed for further enrollment, C_{planned} is the overall number of cases needed for the test, i.e. 381 cases, C_{observed} are the at that stage observed number of cases overall, and ER are the respective event rates assumed for each group, i.e., 8.0% for non-influenza comparator group and 4.0% for QIVc.

For the analysis of for efficacy, an error-spending function will be applied to provide statistical stopping rules for efficacy (α -boundaries) for the first interim analysis and second interim analysis, if necessary, based on the information accumulated until that specific interim stage, i.e. based on the accumulated variance of the parameter of interest.

These boundaries will be calculated on a p-value see:

<https://support.sas.com/documentation/onlinedoc/stat/131/seqdesign.pdf>

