At each interim stage, α -boundaries, forming the adjusted probabilities for the type 1 error, are calculated using error-spending function and if the p-value for the test of primary objective is lower than the respective α -boundary the trial stops for efficacy at this stage.

In other words the trial stops early for efficacy if data collected at this stage allows to demonstrate both primary and co-primary efficacy objectives (reject null-hypothesis). Further guided by efficacy estimates of QIVc described in secondary efficacy objective 4 (prevention of PCR confirmed influenza antigenic matched to the strains selected for the seasonal vaccine). Otherwise, the trial continues to the next stage and more subjects will be enrolled.

The cumulative O'Brien-Fleming type error-spending-function ([Lan and DeMets, 1983](#), option ERRFUNCOBF in SAS[®] PROC SEQDESIGN) will be used for both α - and β -boundaries; the error-spending function is defined as:

$$E(t; a) = \begin{cases} 1 & \text{if } t \geq 1 \\ \frac{1}{a} 2 (1 - \Phi(\frac{z(1-a/2)}{\sqrt{t}})) & \text{if } 0 < t < 1 \\ 0 & \text{otherwise} \end{cases}$$

where a equals α for α spending function and β for beta spending function, and where t is the information fraction.

If the trial proceeds to the final analysis, the boundary for rejection of null hypothesis is identical to the type 1 error (that is as the 0.025 one-sided alpha level) with power specified for the overall design, and the trial stops to either reject or not reject the null hypothesis of the primary objective.

Additional interim analyses may be requested at a future date (by the DMC), particularly if the first interim analysis is conducted soon after 191 cases of influenza have been reported. In this case, the DMC may request that a second interim analysis be conducted to allow for greater accuracy to determine if the trial should stop or continue.

Any modifications of a trial design (i.e. introducing additional interim analysis stage) and calculations of number of subjects to be additionally enrolled will be based on the assumptions as defined in the protocol Section 8.6, and will not be influenced by the results of an interim analysis.

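### Protocol and SAP disagree on whether an interim and a futility test take place and on the final-analysis trigger, and the SAP's example boundaries hold alpha only with a binding futility stop

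*Protocol*

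**What the plan says.** **Whether an interim takes place.** Protocol 8.6 says that at 191 to 380 cases "an unblinded interim analysis for efficacy and futility will be performed by a DMC". Protocol 3.6 adds that "At least one interim analysis will be performed". SAP 14.1 is permissive; its sentence opens "If decided by the Sponsor and after observing at least 50% of planned events meeting the co-primary endpoint, an interim analysis for efficacy may be". SAP 3, 5 and 15 are also permissive.

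**Futility.** Under Protocol 8.6, "if the p-values are higher than the β -boundaries, the trial stops early for futility at that stage". The synopsis sends the detail elsewhere: "Stopping rules for futility and efficacy and any additional details regarding the DMC will be defined in the SAP and in the DMC Charter". Protocol 8.5 and 8.6 repeat that reference. Protocol 8.5 plans O'Brien-Fleming bounds for efficacy and futility, whereas the matching sentence in SAP 5 names efficacy bounds only. SAP 14.1 gives early efficacy as the only reason to stop, and otherwise continues enrolment. Yet its O'Brien-Fleming-type spending function "will be used for both α - and β -boundaries".

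**At 381 or more cases.** The protocol synopsis, 3.1 and 8.6 go directly to unblinding and final analysis. SAP 14.1 adds a second condition: "and subjects have been enrolled over at least three seasons the study will be unblinded". SAP 5 allows extra enrolment when cases are poorly spread over time or geography.

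**Boundaries.** SAP Table 14.1-1 gives an example with 191 and 382 events and one-sided p-value boundaries of 0.00282 (interim) and 0.02518 (final). SAP 14.1 states an overall one-sided alpha of 2.5%.

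**The concern.** The protocol delegates the details of a futility rule to the SAP, and the SAP contains no such rule. The change of wording between Protocol 8.5 and SAP 5 suggests that futility was removed on purpose, but the supplied SAP text does not say so, and the β-boundary wording remains. A DMC reading the protocol would expect an interim and a futility comparison. A DMC reading the SAP might be given neither. The two texts also differ on whether children are still enrolled after the target case count is reached.

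There is a type I error consequence as well. A binding futility stop lets the efficacy boundaries be slightly looser. If futility is dropped and those boundaries are kept, alpha exceeds its stated level.

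**Working it through.** **1. The texts side by side**

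| Situation | Protocol | SAP |
|---|---|---|
| 191-380 cases | Interim for efficacy and futility planned (8.6; at least one interim, 3.6) | Interim only if the sponsor decides; efficacy only (14.1) |
| Weak interim result | Compared with a β-boundary | No threshold or action; enrolment continues |
| 381 or more cases, fewer than three seasons | Final analysis | Condition for final analysis not met; extra enrolment possible (5) |

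**2. Reproducing SAP Table 14.1-1**

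Inputs: information fraction t = 191/382 = 0.5; one-sided alpha 0.025; power about 90% (Protocol 8.5), so β = 0.10. The two test statistics have correlation √0.5 = 0.707.

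Overall alpha = P(Z1 > a) + P(b < Z1 ≤ a, Z2 > c), where a and c are the efficacy boundaries and b is the futility boundary.

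A one-sided O'Brien-Fleming design with efficacy and binding futility boundaries has a = C1/√t, c = C1 and b = δ√t − C2/√t, with δ = C1 + C2. Solving for alpha 0.025 and power 0.90 gives C1 = 1.957 and δ = 3.295, so C2 = 1.338.

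- a = 1.957/0.707 = 2.768, p = 0.00282
- c = 1.957, p = 0.02518
- b = 3.295 × 0.707 − 1.338/0.707 = 0.438, p = 0.331

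Both table entries are reproduced. The other designs tried do not match:

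| Design | Interim p | Final p |
|---|---|---|
| O'Brien-Fleming, efficacy only | 0.00258 | 0.02400 |
| Spending function printed in SAP 14.1, efficacy only | 0.00153 | 0.02450 |
| Same function with β-spending | 0.00153 | 0.02526 |

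Overall alpha with the table's values:
- futility binding at p = 0.331: 0.0250
- no futility stop (b = −∞): 0.0263

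If 0.00282 is kept at the interim with no futility stop, a final boundary of about 0.0239 restores 0.025.

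**3. How often a futility boundary would be crossed**

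Inputs (Protocol 8.5): co-primary null HR 0.70, assumed HR 0.50, 381 events, β = 0.10, half the information. The boundary uses the spending function printed in SAP 14.1.

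- β spent = 2[1 − Φ(1.645/√0.5)] = 0.0200, normal quantile 2.054.
- Information at half = 381 × ¼ × ½ = 47.6 (cases split equally) or 381 × 2/9 × ½ = 42.3 (cases split 2:1, as under HR 0.50).
- Drift = ln(0.70/0.50) × √I = 2.322 or 2.189.
- Futility z = drift − 2.054 = 0.268 or 0.136, one-sided p = 0.39 or 0.45.
- Estimated VE at the cut = 1 − 0.70 × exp(−z/√I) = 32.7% or 31.4%.
- Crossing probability = Φ(z − ln(0.70/HR) × √I).

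| True VE | Co-primary alone | Both objectives must cross |
|---|---|---|
| 30% | 55-61% | 31-47% |
| 40% | 19-21% | 7-13% |
| 45% | 8% | 2-4% |
| 50% | 2% | under 1% |

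The last column applies the same method to the primary objective (null HR 0.80, assumed HR 0.55). It assumes the same 191 cases and true VE in both cohorts, and full primary information at 298 or 382 events.

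With the boundary that reproduces the SAP table (p = 0.331) and the co-primary alone, the cut is an estimated VE of about 34%. The crossing probabilities are then 67%, 27% and 3% at true VE 30%, 40% and 50%.

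**The case against.** **The protocol's stop is not automatic.** Protocol 8.6 leaves the decision to discussion between the DMC and Senior Management and adds clinical and strategic rules. Protocol 3.7 gives the DMC a recommendation only, and 3.6 says there are no predetermined stopping rules beyond those for individual subjects. Protocol 8.2 and 8.4 speak of an interim conditionally. All of this stands. A reader might infer that the same data would necessarily stop the trial under one document and continue it under the other, or that the DMC cannot comply with both. The texts do not support that: an interim performed by the DMC also satisfies the SAP's permissive wording.

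**The SAP does not exclude stopping for a poor result.** A reader might infer a zero chance of a futility stop under the SAP. SAP 14.1 lets the DMC add clinical and strategic stopping rules, and the DMC charter, which may hold a futility rule, was not supplied. What is missing is a statistical futility rule in the SAP.

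**The three-season condition is partly covered.** A reader might infer that 381 or more cases in fewer than three seasons has no provision at all. SAP 5 allows extra enrolment for poor temporal distribution, and SAP 3 plans at least three seasons. SAP 8.5 describes the seed viruses of Seasons 1 to 3 in the past tense, so the case may never arise. The triggers still differ.

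**The table is an example.** SAP 14.1 says the actual boundaries depend on the case count at the interim. That is fair, but the example shows the design apparently behind the calculation, and it differs from the efficacy-only rule in the text.

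**Timing and version.** Protocol 8.6 dates the first two seasons to no later than April 2018. The SAP cites protocol version 5.0 of 13 December 2018, and the version of the supplied protocol cannot be confirmed. This may reduce the practical stakes but does not reconcile the texts.

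**Conclusion.** The concern holds as a conflict between the documents on three points: whether an interim takes place, whether futility is tested, and what triggers the final analysis. SAP 14.1 is also inconsistent with itself, because it names β-boundaries but attaches no action to them.

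The crossing probabilities show that the futility question matters mainly when true VE is well below the assumed 50%. They rest on β = 0.10, half the information and normal approximations. They also depend on which objective governs, which Protocol 8.6 does not state clearly: its efficacy rule uses both p-values, and its futility sentence says only p-values. They are probabilities of crossing a boundary, not of the trial stopping.

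The alpha excess is small, about 0.0263 − 0.025 = 0.0013. It arises if the table's boundaries are used with no futility stop, or with one that is not binding.

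**What to change.** Before any unblinding, put one rule in the protocol (synopsis, 3.1, 3.6, 3.7, 8.5 and 8.6), the SAP and the DMC charter.

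- **If the interim is efficacy-only:** remove futility from the protocol, and remove all β-boundary and β-spending text from SAP 14.1. Make the interim either planned or optional in every document. Recalculate Table 14.1-1: about 0.00153 and 0.02450 with the spending function printed in SAP 14.1, or 0.00282 with a final boundary of about 0.0239. SAP 8.3 prints a different spending function (power parameter 2), so name the one used.
- **If futility is kept:** state the boundary, the objective or objectives it applies to, and whether it is binding. If it is non-binding, calculate the efficacy boundaries without relying on it.
- **In either case:** state the same action in both documents for 381 or more cases before three seasons are enrolled.

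The cost is document wording plus one recalculation of the boundaries. No patients or procedures are added.
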